13.4.2.9 Section 7.4.1.1.1 Adverse device effect (ADE)

Section revised per modification 5.

Old text:

An AE related to the use of Essure, including AEs resulting from insufficient or inadequate instructions for use, deployment, implant (placement), installation or operation or any malfunction of the investigational medical device, use error or from intentional misuse of the medical device.

New text:

An AE related to the use of Essure or NovaSure, including AEs resulting from insufficient or inadequate instructions for use, deployment, implant (placement), installation or operation or any malfunction of the investigational medical device, use error or from intentional misuse of the medical device.

13.4.2.10 Section 7.4.1.1.2 Unanticipated adverse device effect (UADE)

Section revised per modification 6.

Old text:

~~An AE is considered unanticipated if by its nature, incidence, severity or outcome it has not been identified in the IFU.~~

New text:

A serious adverse effect is considered unanticipated if by its nature, incidence, severity or outcome it has not been identified in the IFU.

13.4.2.11 Section 7.4.1.1.2 Serious adverse event (SAE)

Section revised per modification 7.

Old text:

~~An SAE is classified as any untoward medical occurrence but is not related to a medical device that, meets any of the following criteria:~~

- ~~1. Led to death~~
- ~~2. Led to a serious deterioration in the health of the subject that:~~
 - ~~○ resulted in a life threatening illness or injury~~
 - ~~○ resulted in a permanent impairment of a body structure or body function~~
 - ~~○ required hospitalization or prolongation of existing hospitalization~~
 - ~~○ resulted in a medical or surgical intervention to prevent permanent impairment to body structure or function~~

Note: For the purposes of this protocol, ectopic pregnancy and spontaneous abortion are always considered as important events and therefore reported as SAEs.

New text:

An SAE is classified as any untoward medical occurrence that, at any dose, meets any of the following criteria (a – g):

a. Results in deathb. Is life-threatening

The term ‘life-threatening’ in the definition refers to an event in which the subject was at risk of death at the time of the event, it does not refer to an event which hypothetically might have caused death if it were more severe.

c. Requires inpatient hospitalization or prolongation of existing hospitalization

A hospitalization or prolongation of hospitalization will not be regarded as an SAE if at least one of the following exceptions is met:

- The admission results in a hospital stay of less than 12 hours
- The admission is pre-planned
(e.g. elective or scheduled surgery arranged prior to the start of the study; admission is part of the study procedures as described in Section 7.1.2)
- The admission is not associated with an AE
(e.g. social hospitalization for purposes of respite care).

However, it should be noted that invasive treatment during any hospitalization may fulfill the criterion of ‘medically important’ and as such may be reportable as an SAE dependent on clinical judgment. In addition, where local regulatory authorities specifically require a more stringent definition, the local regulation takes precedence.

d. Results in persistent or significant disability / incapacity

Disability means a substantial disruption of a person’s ability to conduct normal life’s functions.

e. Is a congenital anomaly / birth defectf. Is another serious or important medical event as judged by the investigatorg. Requires intervention to prevent permanent impairment of a body function /damage, to a body structure

Note: For the purposes of this protocol, ectopic pregnancy and spontaneous abortion are always considered as important events and therefore reported as SAEs.

13.4.2.12 Section 7.4.1.1.2.2 Unanticipated serious adverse device effect (USADE)

Section revised per modification 8.

Old text:

An unanticipated serious adverse device effect (USADE) is any serious adverse effect on health or safety or any life-threatening problem or death caused by, or associated with, a device, if that effect, problem, or death was not previously identified in nature, severity, or degree of incidence in the investigational plan or application (including supplementary plan or application), or any other unanticipated serious problem associated with a device that relates to the rights, safety, or welfare of subjects.

New text:

An unanticipated serious adverse device effect (USADE) is any serious adverse effect on health or safety or any life-threatening problem or death caused by, or associated with, a device, if that effect, problem, or death was not previously identified in nature, severity, or degree of incidence in the investigational plan or application (including supplementary plan or application), or any other unanticipated serious problem associated with a device that relates to the rights, safety, or welfare of subjects. This is the same definition provided in the UADE Section 7.4.1.1.1.2. This has been corrected above in the UADE definition. However, as both terms have been used at various timepoints in this protocol, the definition is maintained here.

13.4.2.13 Section 7.4.1.1.4 Device deficiency

Section revised per modification 5.

Old text:

Inadequacy of Essure related to its identity, quality, durability, reliability, safety or performance, such as malfunction, misuse or use error and inadequate labeling.

New text:

Inadequacy of Essure or Novasure related to its identity, quality, durability, reliability, safety or performance, such as malfunction, misuse or use error and inadequate labeling.

13.4.2.14 Section 7.4.1.1.4.1 Device failure

Section revised per modification 5.

Old text:

Failure of Essure to perform or function as intended, including any deviations from the performance specifications or intended use (e.g., pregnancy when micro-insert properly located and fallopian tubes occluded; continued menorrhagia despite a completed endometrial ablation procedure). For the purposes of this study, a pregnancy that occurs in a subject told to rely on a commercially available Essure device for contraception is a device failure.

New text:

Failure of Essure or Novasure to perform or function as intended, including any deviations from the performance specifications or intended use (e.g., pregnancy when micro-insert properly located and fallopian tubes occluded; continued menorrhagia despite a completed endometrial ablation procedure). For the purposes of this study, a pregnancy that occurs in a subject told to rely on a commercially available Essure device for contraception is a device failure. For the purposes of this protocol, persistence or recurrence of heavy menstrual bleeding will be considered device failures for the Novasure device.

13.4.2.15 Section 7.4.1.1.4.2 Device malfunction

Section revised per modification 5.

Old text:

Failure of Essure to meet its performance specifications or otherwise perform as intended when used in accordance with the IFU (e.g., difficulties with deployment or detachment of micro-insert; device difficulties when conducting endometrial ablation).

New text:

Failure of Essure or Novasure to meet its performance specifications or otherwise perform as intended when used in accordance with the IFU (e.g., difficulties with deployment or detachment of micro-insert; device difficulties when conducting endometrial ablation).

13.4.2.16 Section 7.4.1.1.5 Important Medical Events and events of special interest

Section revised per modification 9.

Old text:

[...]

- Upper genital tract infections (for example: endometritis, salpingo-oophoritis, salpingitis).
- Expulsion or migration of Essure inserts.

New text:

[...]

- Perforations of the uterus, cervix or fallopian tubes.
- Upper genital tract infections (for example: endometritis, salpingo-oophoritis, salpingitis).
- Expulsion or migration of Essure inserts.
- Potential allergy/hypersensitivity to Essure inserts (for example: itch [pruritus], rash, hives [urticaria], facial edema, angioedema, allergy to metals).

13.4.2.17 Section 7.4.1.3 Assessments and documentation of adverse events

Section revised per modification 10.

Old text:

[...]

Investigators must document all device failures, malfunctions and use errors, including the assessment of whether the event is considered an incident (ADE) using the Device Malfunction and Failure CRF.

~~Investigator must determine whether adverse event is an unanticipated adverse device effect; if so, it must be reported as required by Section 7.4.1.1.~~

Because an approved device will be used for the placement procedure, any device malfunctions will be reported to the sponsor's Product Surveillance department. Device malfunctions will not be analyzed as part of this study as the placement procedure and device are not being evaluated.

New text:

[...]

Investigators must document all device failures, malfunctions and use errors, including the assessment of whether the event is considered an incident (ADE) using the Device Malfunction and Failure CRF.

Because an approved device will be used for the placement procedure, any device malfunctions will be reported to the sponsor's Product Surveillance department. Device malfunctions will not be analyzed as part of this study as the placement procedure and devices are not being evaluated.

13.4.2.18 Section 7.4.1.4 Reporting of serious adverse events

Section revised per modification 12.

Old text:

Investigator's notification of the sponsor

[...]

All SAEs and ~~incidents~~ (ADEs) occurring during the observation period defined in Section 7.4.1.3 must immediately (within 24 hours of the investigator's awareness) be reported to the sponsor. An SAE form must also be completed within 24 hours of the investigator awareness and forwarded to the sponsor's designated recipient.

[...]

Sponsor's notification of the investigational site

[...]

If the adverse event is ~~also~~ an unanticipated adverse device effect, the investigator must report it to the sponsor within 3 working days after the investigator becomes aware of the event. The investigator will send to the sponsor all pertinent paperwork (discharge summaries, office notes, etc.) within 5 working days.

[...]

New text:

Investigator's notification of the sponsor

[...]

All SAEs and SADEs occurring during the observation period defined in Section 7.4.1.3 must immediately (within 24 hours of the investigator's awareness) be reported to the sponsor. An SAE form must also be completed within 24 hours of the investigator awareness and forwarded to the sponsor's designated recipient.

[...]

Sponsor's notification of the investigational site

[...]

If the adverse event is the result of an unanticipated adverse device effect, the investigator must report it to the sponsor within 3 working days after the investigator becomes aware of the event. The investigator will send to the sponsor all pertinent paperwork (discharge summaries, office notes, etc.) within 5 working days.

[...]

13.4.2.19 Section 7.4.2 Device removal

Section added per modification 11.

Old text:

Not applicable

Added text:

Each time a removal procedure is performed, additional information will be collected about the circumstances surrounding the removal (reason for removal, procedure details, any energy sources used, vasoconstrictive agent used, imaging to assist with confirming the location of the insert, and the location and status of the device removed).

Note that the Section numbering inside the Section 7.4 has changed due to this modification.

13.4.2.20 Section 8.6 Determination of sample size

Section revised per modification 1.

Old text:

[...]

Assumptions

The following assumptions were used to calculate the PAS sample size and power for the 1- and 3-year hypothesis:

- Participants in this PAS are women who have undergone the Essure procedure followed by a successful Essure Confirmation Test showing satisfactory micro-insert location and bilateral tubal occlusion;

[...]

New text:

[...]

Assumptions

The following assumptions were used to calculate the PAS sample size and power for the 1- and 3-year hypothesis:

- Participants in this PAS are women who have undergone the Essure procedure followed by a successful Essure Confirmation Test showing satisfactory micro-insert location and bilateral tubal occlusion on HSG OR optimal or satisfactory micro insert location on TVU;

[...]

13.4.2.21 Section 14 Appendices

Section revised per modification 12.

Old text:

~~Appendices A-D were to be distributed to all sites with the protocol and were not attached to this amendment to reduce redundancy.~~

Appendix E: Detailed Study Timelines

Revised/projected study milestones based on enrollment rates:

[...]

New text:

All appendices from prior protocol amendments (Essure IFU, NovaSure Instructions for Use and Controlled Operator's Manual, Case Report Form and the Informed Consent) have been distributed to the sites with previous protocol versions and are therefore not attached here to avoid redundancy.

15. Detailed Study Timelines

Revised/projected study milestones based on enrollment rates:

[...]

14. Appendices - *amended*

All appendices from prior protocol amendments (Essure IFU, NovaSure Instructions for Use and Controlled Operator's Manual, Case Report Form and the Informed Consent) have been distributed to the sites with previous protocol versions and are therefore not attached here to avoid redundancy.⁵⁵

15. Detailed Study Timelines

Revised/projected study milestones based on enrollment rates:

| | |
|---|--|
| Study start date – First subject enrolled | NOV 2012 |
| Expected subject enrollment at 12 sites (subjects/month/site) | 0.4 |
| Expected subject enrollment rate per year | 43 based on 9 current sites able to enroll |
| Expected subject enrollment completion date | DEC 2017 |
| Expected final subject follow-up date | JAN 2021 |
| Expected completion of final post-approval study report | JUL 2021 |

⁵⁵ Text modified per Amendment 6.

ADE	Adverse device event
ADL	Activities of daily living
AE	Adverse event
CRF	Case Report Form
D&C	dilatation and curettage
EA	Endometrial Ablation
ECG	electrocardiogram
eCRF	Electronic case report form
EMA	European medicines evaluation agency
FDA	Food and Drug Administration of the United States
GCP	Good clinical practices
HSG	Hysterosalpingogram
HTA	Hydro Thermablator [®]
ICF	Informed consent form
IEC	Independent ethics committee
IFU	Instructions for Use
IME	Important medical events
IRB	Institutional Review Board
IVRS	Interactive voice response system
LPLV	Last patient last visit
PAS	Post-Approval Study
PMA	Pre-market Approval
SADE	Serious adverse device effect
SAE	Serious adverse event
UADE	Unanticipated adverse device effect
USADE	Unanticipated serious adverse device effect
US	United States

1. Introduction

This statistical analysis plan is based on Amendment 6 of the protocol (dated 12 Jul 2016). Statistical analyses will be performed by or under supervision of the responsible statistician at Bayer HealthCare Pharmaceuticals.

The purpose of the study is to evaluate the effectiveness and safety of the Essure System when a NovaSure endometrial ablation (EA) procedure is performed following a successful Essure Confirmation Test. This post-approval study (PAS) is a prospective, multi-center, single-arm observational study.

2. Study Objectives

The objectives of this study are to:

- Evaluate the contraceptive failure rate of Essure when NovaSure is performed following a successful Essure Confirmation Test, and
- Monitor the incidence of adverse events and/or complications associated with the performance of NovaSure in the presence of Essure micro-inserts.

3. Study Design

Design overview

This PAS is a prospective, multi-center, single-arm observational study to monitor and evaluate the effectiveness and safety of Essure when NovaSure is performed following a successful Essure Confirmation Test. The PAS will be conducted at up to 15 sites in the United States. Each site may enroll a maximum of 35 subjects. A minimum of 220 female subjects will be enrolled in the study. Subjects will be followed for a total of 3 years post-NovaSure EA with evaluations to occur at the 1 week, 12 month, 24 month and 36 month follow-up time points. PAS subjects who have been identified as candidates for NovaSure EA and have had a successful Essure Confirmation Test will be considered.

At least 50% of the subjects enrolled in the study must be 45 years of age or younger.

End of study

The primary outcome will be collected after last patient - last visit (LPLV). The end of the study as a whole will be the date when the clean data base is available.

3.1 Primary Endpoint

- Occurrence of confirmed pregnancy at 1 year and 3 years among subjects relying on Essure micro-inserts for permanent birth control when NovaSure is performed following a successful Essure Confirmation Test.

3.2 Secondary Endpoints and Assessments

- Adverse event data

3.3 Study Flowchart

See Section 7.1.1 in the Study Protocol for a schedule of procedures.

4. General Statistical Considerations

4.1 General Principles

The statistical evaluation will be performed by using the software package SAS release 9.2 or higher (SAS Institute Inc., Cary, NC, USA) or R release 3.0.2 or higher (R Foundation for Statistical Computing, Vienna, Austria). Baseline NovaSure EA and follow-up data will be summarized using the appropriate statistical method; continuous variables will be summarized using means, standard deviations, medians and quartiles. Categorical data will be summarized using frequency rates (e.g., count/sample size).

4.2 Handling of Dropouts

A subject who discontinues study participation prematurely for any reason is defined as a “dropout” if the subject qualified for the study or attempted the NovaSure EA procedure. Dropouts will be analyzed in each analysis set for which they meet the qualifications. Dropouts will not be replaced.

A subject who, for any reason (e.g. failure to satisfy the selection criteria), terminates the study before the time point used for the definition of “dropout” (see above) is regarded a “screening failure”.

Any subject removed from the trial will remain under medical supervision until discharge or transfer is medically acceptable.

4.3 Handling of Missing Data

In order to achieve the goal of a well conducted clinical trial according to Good Clinical Practice (GCP), every effort will be made to collect all data. i.e., if a subject misses a

scheduled assessment, the site personnel will contact the subject and request her to come to the clinic for a visit. However, despite best efforts, it may be inevitable that missing or incomplete data are reported. Except as noted below, missing data will not be estimated or imputed.

General rules

When appropriate, the following rules will be implemented so as not to exclude subjects from statistical analyses due to missing or incomplete dates:

Table 1 - Imputation rules for missing adverse event start and stop dates

Scenario		
Start date	Stop date	Imputation rule
Partially Missing	Complete	
Imputation of start date:
 
A. If partial date has day and month missing: If the year is same as the year of the NovaSure EA procedure, then the day and month of the NovaSure EA procedure will be assigned to the missing fields If the year is prior to the year of the NovaSure EA procedure, then December 31 will be assigned to the missing fields. If the year is after the year of the NovaSure EA procedure, then January 01 will be assigned to the missing fields.
 
Note: if NovaSure EA procedure date is missing, then there is no need to impute the date as the AE is not treatment emergent.
 
B. If partial date has missing day only: If the month and year are same as the year and month of the NovaSure EA procedure, then the day of the NovaSure EA procedure will be assigned to the missing day.

		
If the month and year are before the year and month of the NovaSure EA procedure, then the last day of the month will be assigned to the missing day.
 
If the month and year are after the year and month of the NovaSure EA procedure, then the first day of the month will be assigned to the missing day.
 
If the imputed event start date (after A or B above) is after the event stop date, the start date will be imputed to be equal to the stop date.

Complete	Partially Missing	
Imputation of stop date
 
C. If partial date has day and month missing:
 
If the year is same as the year of the NovaSure EA procedure, then the day and month of the NovaSure EA procedure will be assigned to the missing fields
 
If the year is prior to the year of the NovaSure EA procedure, then December 31 will be assigned to the missing fields.
 
If the year is after the year of the NovaSure EA procedure, then January 01 will be assigned to the missing fields.
 
D. If partial date has missing day only:
 
If the month and year are same as the year and month of the NovaSure EA procedure, then the day of the NovaSure EA procedure will be assigned to the missing day.
 
If the month and year are before the year and month of the NovaSure EA procedure, then the last day of the month will be assigned to the missing day.
 
If the month and year are after the year and month of the NovaSure EA procedure, then the last day of the month will be assigned to the missing day.

		If the imputed stop date (after C or D above) is before the event start date, the stop date will be imputed to be equal to the event start date.
Partially Missing	Partially Missing	Impute start date per A and B above Impute stop date per C and D above If start date > stop date, then set start date = stop date = minimum of (imputed start date per A and B, imputed stop date per C and D)
Partially Missing	Completely Missing	Impute start date per A and B above Impute stop date as the study completion date If start date > stop date, then set start date = stop date = imputed start date per A and B
Completely Missing	Partially Missing	Impute start date as the NovaSure EA procedure date. Impute stop date per C and D above If start date > stop date, then set start date = stop date = minimum of (imputed start date per A and B, imputed stop date per C and D)
Completely Missing	Complete	Impute start date as the NovaSure EA procedure date If start date > stop date, then set start date = (complete) stop date
Completely Missing	Completely Missing	Impute start date as the NovaSure EA procedure date Impute stop date as the study completion date

4.4 Interim Analyses

Interim PAS status reports will be submitted at least annually from the date of the pre-market approval (PMA) letter or other negotiated starting date (i.e., PAS initiation). Ongoing interim PAS status reports will be submitted until the final PAS report is written after the termination or completion of the PAS. The ongoing interim reports and final PAS report will include information related to PAS methodology and results/endpoints including the following:

- Occurrence of confirmed pregnancy at 1 and 3 years after NovaSure EA among subjects relying on Essure inserts for permanent birth control when NovaSure is performed following a successful Confirmation Test.
- Adverse event data.

4.5 Data Rules

Repeated measurements

If there are repeated measurements at one time point, the following rules apply :

- at screening and at baseline the last measurement (based on the specimen collection date and time), ie, the measurement, which is the closest to the attempted NovaSure EA procedure, will be used,
- during or after the attempted NovaSure EA procedure, the first measurement (based on collection date and time) will be used, provided the data are of equal quality.

4.6 Validity Review

Assignment of subjects to the analysis set described in Section 5 will be discussed and documented. In addition, protocol deviations will be discussed, reviewed, and categorized. Any changes to the statistical analysis prompted by the results of this meeting will be documented in an amendment and, if applicable, in a supplement to this SAP.

5. Analysis Sets

Primary effectiveness cohort

All subjects who sign a study-specific ICF and undergo insertion of the NovaSure device transcervically

Primary safety cohort

All subjects who sign a study-specific ICF and in whom a NovaSure procedure is attempted (e.g., subject who comes to the study site with the intent of having the procedure performed).

Enrolled cohort

The enrolled cohort includes any subject who signs the study-specific ICF.

6. Statistical Methodology

Variables measured on metrical scales will be summarized by use of descriptive statistics (number of subjects with non-missing observations, mean, standard deviation, minimum, 1st quartile, median, 3rd quartile, and maximum). Variables measured on ordinal or nominal scales will be summarized by use of frequency tables showing the number and percentage of subjects falling within a particular category.

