5.2 Withdrawal of subjects from study²¹

5.2.1 Withdrawal²² - amended

Subjects *must* be withdrawn from the study for the following reasons:

- At their own request or at the request of their legally acceptable representative
- At any time during the study and without giving reasons, a subject may decline to participate further. The subject will not suffer any disadvantage as a result.
- If, in the investigator's opinion, continuation of the study would be harmful to the subject's well-being

Subjects may be terminated from the study by the Investigator. Reasons for termination of a subject from the study may include, but are not limited to, the following:

- Subject does not retain device (e.g. due to removal of device, expulsion, salpingectomy or other utero-tubal surgeries)

¹⁹ Per Amendment 4 and 5

²⁰ Per Amendment 4

²¹ New section from sponsor template per Amendment 4

²² Withdrawal criteria adapted to suit a device meant for permanent wearing per Amendment 6.

- Death
- An adverse event (AE) preventing study participation
- Lost to follow-up and inability to contact the subject. Note that if a subject who is lost to follow-up is re-contacted, the subject will not be considered to have withdrawn from the study.

A subject who discontinues study participation prematurely for any reason is defined as a “dropout” if the subject has already undergone the NovaSure procedure.

A subject who, for any reason (e.g. failure to satisfy the selection criteria), terminates the study before the time point used for the definition of “dropout” (see above) is regarded a “screening failure”.

Any subject removed from the trial will remain under medical supervision until discharge or transfer is medically acceptable.

In all cases, the reason for withdrawal must be recorded in the case report form (CRF) and in the subject's medical records.

Details for the premature termination of the study as a whole (or components thereof [e.g. centers, treatment arms, dose steps]) are provided in Section 10 (Premature termination of the study).

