8.2 Analysis sets⁴⁵

Primary effectiveness cohort

All subjects who meet study entry criteria, sign a study-specific ICF, and undergo insertion of the NovaSure device transcervically.

Primary safety cohort

All subjects in whom a NovaSure procedure is attempted.

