6.1 Population characteristics

Subject enrollment and disposition will be summarized for the following via the enrolled cohort:

- Enrollment by site and overall
- Disposition (completed study (Y/N), etc.)
- Summary of all reasons for early termination
- Subject validity
- Visit accountability (enrolled subjects not screen failures)

The following demographic and baseline characteristics will be summarized descriptively for the Safety Cohort:

- Demography – Race, ethnicity, age, age groups (18-27, 28-33, >34, and also ≤ 45 , >45), weight [kg], height [cm], and body mass index [kg/m²]
- Medical History – Primary method of contraceptive used immediately prior to the Essure placement procedure, gravidity (both categorical and continuous), parity (both categorical and continuous), vaginal births (categorical only), cesarean births (categorical only), total abortions (categorical only), ectopic pregnancies (categorical only), days from last delivery/termination of pregnancy to NovaSure procedure, days from Essure procedure to NovaSure procedure, days from Essure confirmation test to NovaSure procedure, did Essure confirmation test show both micro-inserts in the

proper location (Y/N), did Essure confirmation test show both fallopian tubes occluded (Y/N), number of previous abdominal surgeries (continuous only), days from most recent abdominal surgery to NovaSure procedure,

- Pelvic exam (unremarkable/remarkable)

The following procedure data will be summarized descriptively for the Primary Effectiveness Cohort:

- NovaSure Procedure – Duration (minutes), anesthesia type (inhaled, IV, IM, oral, regional, local, other), uterine positions (Anteverted, Retroverted, Midpositional), cervical dilation required (Y/N), treatment time (seconds), power setting (continuous), was the ablation procedure interrupted during the treatment cycle (Y/N), was a restart of the endometrial ablation necessary (Y/N), was resistance encountered during withdrawal of the NovaSure device (Y/N), was an Essure micro-insert attached to the array upon removal (Y/N), was the endometrial ablation completed successfully (Y/N)
- Frequency summary of discharge medications

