6.2.2 Secondary Endpoint Analyses

The secondary endpoint in the PAS is the incidence of adverse events when NovaSure EA is performed in the presence of Essure micro-inserts. There is no specific study hypothesis. Instead, the safety profile will be analyzed using summary statistics on the Safety Cohort as described in Section 6.3.

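### The SAP counts arriving with intent as an attempted NovaSure procedure, so unexposed women can enter the adverse-event denominator; separately, the SAP and protocol disagree on who is a dropout

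*SAP*

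**What the plan says.** **Safety cohort.** Protocol section 8.2 defines it as "All subjects in whom a NovaSure procedure is attempted" and does not define an attempt. SAP section 5 uses the same idea, adds a signed consent form, and illustrates an attempt by a "subject who comes to the study site with the intent of having the procedure performed". SAP 6.2.2 describes the secondary endpoint as the "incidence of adverse events when NovaSure EA is performed in the presence of Essure micro-inserts" and says that "the safety profile will be analyzed using summary statistics on the Safety Cohort".

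**Dropouts.** Under protocol section 5.2.1, a woman who leaves early is a dropout "if the subject has already undergone the NovaSure procedure"; one who leaves before that point is a screening failure. Under SAP 4.2 she is a dropout "if the subject qualified for the study or attempted the NovaSure EA procedure". SAP 4.2 adds: "Dropouts will be analyzed in each analysis set for which they meet the qualifications".

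**Visits.** SAP 6.1 lists "Visit accountability (enrolled subjects not screen failures" among the disposition summaries, so this population depends on where the screening-failure line falls.

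The SAP states that it is based on protocol Amendment 6. Its section 7 lists two versions and gives no reason for either difference.

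**The concern.** The secondary endpoint concerns AEs when NovaSure is performed. A woman who arrives and goes home untreated tells us nothing about that, yet the SAP's example places her in the denominator. She cannot contribute a NovaSure-related event, so each such woman lowers the reported incidence. In a single-arm study with no safety hypothesis, these descriptive percentages are the safety result.

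Such women are foreseeable. Protocol Table 7–1 puts the urine pregnancy test and an eligibility re-check on Day 0 before the ablation. Protocol 7.1.2.2 makes a woman ineligible if her uterine cavity measures too small that day.

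The dropout wording raises a different problem. The same woman, qualified but never treated, has opposite status in the two documents. Under the SAP she stays in the visit-accountability population although no follow-up visit can fall due for her.

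**Working it through.** The plan gives no figure on this point, so there is none to reproduce. The check compares the definitions and then sizes the effect under stated assumptions.

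**Step 1: can an unexposed woman enter the safety cohort?** Yes. She signs consent, arrives on Day 0 intending to have the procedure, and is stopped by a pre-procedure check. She matches the SAP's example with no NovaSure device used.

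**Step 2: do the SAP's other rules fit her?** No.
- The note in SAP 4.3, Table 1, says that an AE is not treatment emergent if the NovaSure date is missing. SAP 6.3.1 tabulates treatment-emergent serious AEs. She is in that denominator but cannot be in the numerator.
- SAP 6.1 summarises the interval from Essure placement to NovaSure on the safety cohort. For her the interval does not exist.

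**Step 3: size for the AE tables.** Let N be the women treated and k the women who arrived but were not started. If they add no event, reported incidence = true incidence × N/(N+k), and the relative understatement is k/(N+k). Assumptions: N = 220 (the protocol's minimum enrolment, used here as the number treated) and a true incidence of 10% (22/220). The values of k are illustrative.

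| k | N/(N+k) | 10% is reported as | Relative understatement |
|---|---|---|---|
| 0 | 220/220 = 1.000 | 10.00% | 0% |
| 5 | 220/225 = 0.978 | 9.78% | 2.2% |
| 11 | 220/231 = 0.952 | 9.52% | 4.8% |
| 22 | 220/242 = 0.909 | 9.09% | 9.1% |

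The SAP also tabulates AEs that reach 1% of subjects. The minimum count is (N+k)/100 rounded up, which is 3 women throughout this range, so that list does not change.

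**Step 4: does the dropout wording add to this?** No. SAP 4.2 admits dropouts only to sets whose definition they meet. A woman who qualified and never came meets neither the safety nor the effectiveness definition. Only the example in SAP section 5 changes the safety cohort.

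**Step 5: visit accountability.** Let m be the women who qualified but never had NovaSure. This is not the same count as k, and it is not given either. Protocol 7.1.2.3 and 7.1.2.4 time every follow-up contact from the NovaSure date, so these women have no visit due. If the denominator is nevertheless everyone who is not a screening failure, completion is multiplied by N/(N+m). With an assumed 90% one-year completion (198/220):
- m = 5: 198/225 = 88.0%
- m = 11: 198/231 = 85.7%
- m = 22: 198/242 = 81.8%

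The SAP does not say how due visits are counted, so this step is conditional.

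**The case against.** **The protocol leaves an attempt undefined, so the SAP only illustrates an open term.** True: the safety-cohort difference is a broadening by example, whereas the dropout difference is a direct contradiction. An inclusive safety set can also be defended, because anesthesia or cervical dilation can cause harm before the device is inserted. That supports keeping women in whom the procedure had begun. It does not support keeping women in whom nothing was done. A woman stopped at the cavity check may already have had anesthesia or instrumentation; if so, she belongs in the cohort and is not part of k.

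**There are partial safeguards.** SAP 4.6 requires assignment to analysis sets to be discussed and documented, and SAP 6.1 tabulates disposition and summarises procedure data on a cohort that requires device insertion. A careful reader could approximate the exposed denominator. But the review meeting applies the written definition; it does not correct it.

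**Stronger readings that the documents do not support.**
- A reader might infer that all AE incidence is biased low. Protocol 7.4.1.3 collects AEs from consent, so an untreated woman can add an event to the table of all AEs. The direction is certain only for NovaSure-related and treatment-emergent events.
- A reader might infer that untreated women are scored as missing every visit. The SAP does not say so.
- A reader might infer that a woman with a positive Day 0 pregnancy test is plainly a dropout. Both documents give failure of the selection criteria as an example of a screening failure, so her status under the SAP is arguable.
- A reader might infer an effect on the contraceptive failure rate. The primary effectiveness cohort requires transcervical insertion of the device, so there is none.

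**Conclusion.** The point holds, and it is minor. The SAP's example lets unexposed women into the denominator for AE incidence. NovaSure-related and treatment-emergent incidence is then understated by N/(N+k): about 2% to 9% in relative terms for k of 5 to 22, if 220 women are treated and the added women contribute no such event. At a true incidence of 10%, that is at most about 0.9 percentage points in this range. Because k is not in the documents, the actual effect cannot be derived and may be negligible.

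The conflict over dropouts is real and independent of the first point. It leaves the safety cohort untouched. It would lower reported follow-up completeness only if the denominator is everyone who is not a screening failure, whether or not a visit was due.

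**What to change.** 1. In SAP section 5, delete the example and define an attempt as the NovaSure procedure having begun, meaning anesthesia or first instrumentation for it. List AEs in women who arrived but were not started separately, so that no event is lost.
2. Reconcile SAP 4.2 with protocol 5.2.1 to a single boundary between dropout and screening failure. The protocol's boundary is "if the subject has already undergone the NovaSure procedure". State explicitly where a woman belongs if her procedure was begun but not completed, since the protocol's wording leaves that open.
3. In SAP 6.1, count follow-up visits as due only for women who had NovaSure.

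The cost is a few sentences in the SAP, a slightly smaller safety cohort and one extra listing. No new data are needed.
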